WA Department of Labor and Industries (DLI). The DLI State Fund provides WC insurance for over 2/3 of workers in WA (the remainder work for large self-insured companies and will be excluded due to insufficient available data). Roughly 93,000 State Fund WC claims are accepted annually. Of these, almost 20% involve time loss benefits. Of all accepted WC claims, 32% are women and 68% are men. Overall, about 21% are ≤ 24 years old at injury, 27% are 25 to 34, 24% are 35 to 44, 19% are 45 to 54, and 9% are 55 or older. Race and ethnicity are not recorded; however, in our prior research, approximately 70% of workers were white, 16% were Latino, and 13% reported other racial or ethnic backgrounds. In WA in 2016, there were over 11,000 workers with opioid prescriptions in the first 6 weeks after injury.

OH Bureau of Workers' Compensation (BWC). The BWC is the largest state-fund insurance system in the U.S. and one of the top 10 largest underwriters of WC insurance in the nation, insuring about 60% of OH's workforce. The volume of injured workers in OH is quite similar to WA. The BWC State Fund has about 90,000 accepted claims per year, and about 12% involve time loss benefits. Overall, 36% are

women and 64% are men. About 15% are \leq 24 years old at time of injury, 23% are 25 to 34, 20% are 35 to 44, 22% are 45 to 54 and 20% are 55 or older. The BWC does not collect data on race or ethnicity. In the BWC State Fund, there is an approximate annual prevalence of 20,000 opioid users.

Inclusion Criteria

Aims 1 & 2. Injured workers in OH and WA who (1) file a new accepted State Fund claim, and (2) fill at least one opioid prescription, paid for by WC, during the first 6 weeks after date of injury. The denominator for both time series described in the Analytical Methods section (Aim 1. Analysis Topic A) has the same inclusion criteria, except that criterion (2) does not apply. The same criteria—including criterion (2)—apply to the numerator for the first time series. The numerator for the second time series described is similar, except that criterion (2) is instead the presence of unsafe opioid prescribing during the subacute phase (6-12 weeks).

Aim 3 key informants. Policy makers and stakeholders who were involved in the creation and implementation of the WA or OH ORP.

Aim 3 provider in-depth interviews. Providers that had at least one patient whose opioid prescription paid for through WC had been reviewed in accordance with the state's ORP.

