Aim 3 patient in-depth interviews. Patients who had an opioid prescription for at least 6 weeks paid for by WC or whose prescription payments have been reviewed in accordance with the state's ORP.

Exclusion Criteria

Aims 1, 2, & 3 (patient in-depth interviews only). Injured workers who are under 18 years of age.

Aims 1 & 2. Current cancer diagnosis and (for surveys only) non-English or -Spanish speakers, physically or mentally incapable of completing the survey, incarcerated, or deceased.

Aim 3. Non-English speakers.

Number of Study Groups/Cohorts

The primary analysis involves 2 groups/cohorts of injured workers, 1 from WA and 1 from OH. Secondary analyses involve two subgroups of injured workers within WA, defined by whether the injured worker's attending provider participates in Centers of Occupational Health and Education (COHE) care delivery.

Enrollment/Sample Size

Aims 1 & 2. The time series for Aim 1 will be based on data for all injured workers in OH and WA who file a new State Fund claim from January 1, 2010 through December 31, 2020. For the prospective cohort analysis, we anticipate including 4,636 eligible workers in WA and 779 in OH for a one-year cohort. Using WC claims, pharmacy billing data, and potentially prescription drug monitoring program (PDMP) data from each state, we will track opioid prescribing for each injured worker for a full year after date of injury. The worker survey will largely be drawn from this cohort, depending on the length of time needed to conduct an adequate number of surveys. All workers will be interviewed initially at 4-6 weeks

after injury (baseline). Workers who complete the baseline survey in the first year of recruitment will be asked to complete follow-up surveys at 6- and 12-months after injury. Workers who complete the baseline survey after the first year of recruitment will be asked to *only* do the 6-month follow-up survey due to time constraints. We anticipate that roughly 3,120 workers in WA and 525 workers in OH will complete baseline surveys. We anticipate roughly 1,700 completed 12-month outcome surveys from WA and 234 from OH.

Aim 3 key informants. No more than 12 interviews in WA, supplemented with policy documents to add detail. In OH, we will start with policy documents and use key informant interviews with individuals outside of BWC to complement and supplement the historical account.

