The resulting four time series will be inspected to identify secular trends and discontinuities/unexpected changes that might indicate a policy or regulatory action, or an external factor that might have affected opioid prescribing pattern. A timeline of opioid-related policy events affecting WA and/or OH (e.g., legislation, regulations, guidelines, large-scale interventions) will be constructed and overlaid on these time series to assess patterns and potential confounding related to the state-based environments. As part of Aim 3 (described below), qualitative methods will be used to understand the causes of unexplained fluctuations.

Finally, we will test whether implementation of the WA PA program (implemented in July 2013) or the OH RR program (implemented in March 2019) was associated with a statistically significant reduction in the rate of unsafe opioid prescribing using standard interrupted time series analysis (ITSA) techniques.^{1,2}

Aim 1. Analysis Topic B: Compare PA to RR with respect to unsafe opioid prescribing

This analysis is focused on the primary outcome for this study, unsafe opioid prescribing (defined earlier), using administrative data for the full WA and OH cohorts. We are planning for a one-year prospective timeframe, beginning July 2019 (based on dates of injury). Our cohort size estimates are 4,636 eligible workers in WA and 779 in OH .

Using WC claims and billing data from each state, we will track opioid prescribing for each injured worker for a full year after date of injury in order to test Hypothesis 1: Prospective PA with hard stops (WA) will be associated with statistically significantly less unsafe opioid prescribing compared to RR and prescriber notification (OH).

The primary outcome is the composite unsafe prescribing measure (i.e., meeting one or more of the 3 chronic-phase criteria in Table 1), modeled longitudinally over the three 3-month time windows, in order to assess the comparative effectiveness of PA/RR on the transition from early opioid therapy to longer-term unsafe opioid prescribing. Generalized estimating equations (GEE) panel models will be used to account for outcomes being measured during several time windows within individual patients.³

¹ Linden, A. (2015). Conducting interrupted time series analysis for single and multiple group comparisons. *The Stata Journal*, 15(2), 480-500.

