² Penfold, R. B., & Zhang, F. (2013). Use of interrupted time series analysis in evaluating health care quality improvements. *Acad Pediatr*, 13(6 Suppl), S38-44.

³ Aloisio, K. M., Swanson, S. A., Micali, N., Field, A., & Horton, N. J. (2014). Analysis of partially observed clustered data using generalized estimating equations and multiple imputation. *Stata J*, 14(4), 863-883.

The working correlation structure will be specified as exchangeable (this may be adjusted later in the Statistical Analysis Plan), and robust variance estimates will be used. (Though using the wrong correlation structure can be inefficient, GEE is not highly sensitive to using the wrong correlation structure, as long as there are at least 100 patient clusters and robust variance estimates are used—we expect to have over 3,000 patient clusters.)

The primary predictor is binary (1 for WA cases, 0 for OH cases). The GEE logit link function will be used to test the Aim 1 hypothesis, with unsafe opioid prescribing specified as a binary dependent variable in each time window. These regression models will provide an estimate of the odds of unsafe opioid prescribing in WA compared to OH, controlling for baseline differences in the two groups. The subacute phase measure, and also each individual component of the composite measure (i.e., chronic use, concurrent sedatives, high dose), will also be tested as distinct outcomes, which will provide information on potential variation in mechanisms and timing of ORP effect across WA and OH. Time will be included in the models (assigning an indicator for quarter since the date of injury; 0, 1, 2, 3), and interacted with state in order to assess (1) change in unsafe opioid prescribing over time and (2) differences in such change by state.

Covariates will be reassessed after more information is available regarding the availability, completeness, and cross-state comparability of various data fields in the OH data. Our initial plan is to include the following covariates for this analysis topic:

- Age
- Gender
- Pre-injury wage
- Marital status
- Number of dependent children
- Injury type
- Occupation
- Industry
- Rural/urban residence
- Provider type, specialty, and COHE or ECP affiliation
- Functional Comorbidity Index (FCI) and cancer diagnosis, based on WC billing data
- PDMP data, if available (see Analysis Topic D), will be used to control for opioid prescriptions in the 3 months prior to injury

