This analysis is focused on the secondary and exploratory patient outcomes for this study, using administrative and survey data for the WA survey sample. Surveys will be conducted at approximately 6 weeks (baseline), 6 months, and 12 months after injury. Our estimates are rough and will be updated as survey enrollment proceeds. However, we anticipate that roughly 3,120 workers in WA will complete baseline surveys, that roughly 1,700 will completed 12-month outcome surveys, and that approximately half of those interviewed will have an attending provider affiliated with COHE.

This analysis will test Hypothesis 2A (stated above) with respect to patient outcomes, using parallel analyses to those described in Analysis Topic H. Most secondary and exploratory patient outcomes will be based on survey data, but several will be based on WC data (see Tables 2 and 3). The only adjustments to Analysis Topic H are that models will include only the WA survey sample, and the binary primary predictor and propensity score calculations will be based on COHE status rather than on state jurisdiction (1 for COHE, 0 for non-COHE).

Additional Information Relevant to Quantitative Analyses for Aims 1, 2, and 2A

Subgroups of Interest

Planned subgroup analyses are listed under the relevant analysis topics above. Because all subgroup analysis will be exploratory, non-exhaustive examples of potential subgroups have been specified. New subgroups of interest may be identified via exploratory data analysis and/or proposed ad hoc by the principal investigator, co-investigators, or stakeholders. The total number of subgroup analyses—and all subgroups and outcomes analyzed—will be reported, along with subgroup definitions and procedures used. If indicated, multiple comparisons will be accounted for using p-value adjustment.

Operational Definitions for Eligibility Criteria

These definitions will need to be aligned as much as possible across the two states. The following operational definitions are based on our history of working with WA WC data. They may need to be modified after preliminary OH WC data are available for inspection.

- Inclusion criteria:
 - New State Fund claim: Identified by each state WC agency
 - At least one opioid prescription during the first 6 weeks after date of injury: Based on WC pharmacy billing data
 - Ability to speak English or Spanish (for the survey only): This will be determined by interviewers during the contact/consent process
- Exclusion criteria:

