Raw administrative data (i.e. WC claims data, pharmacy billing data, and PDMP data) will be received from the Washington and Ohio workers' compensation systems. These files will be kept in separate folders for each state and designated as read-only so that they cannot be changed. A log in Microsoft Excel in each folder will keep track of these files as they come in and will include date and time received, size, description, and other relevant meta-data.

Similarly, survey data will be received from the Survey Research Division, stored as a read-only file in a separate folder, and tracked via a log in Microsoft Excel with relevant meta-data.

Merged data files for analysis will be read-only and stored in a separate folder. This folder will also have a log in Microsoft Excel that contains the meta-data in order to keep track of the latest version. This folder will be accessible by team members doing the statistical analysis. All analysis work will be kept in folders separate from the data folders.

Data handling

The Data Manager(s) will be responsible for managing the data, including de-identifying and merging datasets. In both states, each WC claim has a unique Claim ID and a unique Claimant ID, allowing for the identification of multiple claims by one patient. Data files for the WC claims data and pharmacy billing data will be linked using these IDs.

After merging datasets, the Claim ID and Claimant ID will be replaced with Study IDs. A separate linkage file with the Claim ID and the Study ID will be retained and will be stored in a separate folder only accessible by the Data Manager(s), Research Coordinator, and Project Director.

Administrative workers' compensation data will be stripped of most direct patient identifiable information before it is received by this project. For surveys and individual in-depth interviews, some identifiable information (e.g. name, address, phone number) will be necessary for recruitment. The Data Manager(s) will produce deduplicated lists of recruitment targets for the baseline study for the Survey Research Division. The recruitment lists will include the UW-created Study ID, as well as the information necessary for recruitment. Survey data received back from the Survey Research Division will contain the study ID (but not the identifiable information).

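### Topic B is read as transition to long-term opioid use, but the cohort has no opioid-free look-back and the only named control for pre-injury use depends on PDMP data that are not yet assured

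*Combined protocol and SAP*

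**What the plan says.** **Entry.** Section 4 (Inclusion Criteria) requires a new accepted State Fund claim and that the worker "fill at least one opioid prescription, paid for by WC, during the first 6 weeks after date of injury". The operational definition in Section 7 adds no window before injury: "At least one opioid prescription during the first 6 weeks after date of injury: Based on WC pharmacy billing data". Exclusions for Aims 1 and 2 are age under 18 and, in the plan's words, "Current cancer diagnosis and (for surveys only) non-English or -Spanish speakers", followed by further survey-only criteria. Opioid use before injury is not among them.

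**Outcome.** The Table 1 composite is met by any one of three chronic-phase metrics at 3-6, 6-9 or 9-12 months. None requires new onset. It is measured from WC pharmacy billing, with PDMP data for validation.

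**Purpose.** Topic B models this composite to assess the "effectiveness of PA/RR on the transition from early opioid therapy to longer-term unsafe opioid prescribing".

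**Control for prior use.** The Topic B covariate list has one item: "PDMP data, if available (see Analysis Topic D), will be used to control for opioid prescriptions in the 3 months prior to injury". The list is described as an initial plan, to be reassessed once OH data are seen. The added survey covariates in Topic H, which Topic C also uses, do not include pre-injury opioid use; treatment for pain is the nearest item.

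**PDMP availability.** Topic D says feasibility is still being confirmed. Appendix A (Linkage of PDMP data) describes routine monthly linkage with full record history in WA. OH has no batch delivery yet, but has statutory authority to receive the data, and individual look-up is the stated fallback.

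**Another source.** Appendix A (Data handling) says, for WA and OH alike, that "each WC claim has a unique Claim ID and a unique Claimant ID, allowing for the identification of multiple claims by one patient". No use of this for prior opioid exposure is planned.

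**The concern.** Opioid use before injury is likely to be a strong predictor of opioid use 3 to 12 months later. A worker with a long-standing prescription, for example on an older claim, can enter on a new injury, fill an opioid in the first six weeks and then meet the composite. Nothing has changed after the new injury, yet the worker is counted as having an unsafe outcome under the state's program.

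There are two consequences for Hypothesis 1:

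- **Unequal shares.** If prior users are a larger part of one state's cohort, a WA-OH difference can appear, or a real one can be hidden, without any program effect.
- **Equal shares.** The comparison is not confounded, but prior users contribute outcome events that are not transitions. If the programs affect them less than they affect new users, the estimate moves towards 1.

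The PDMP covariate would address the first consequence only if both states supply the data. If only one state does, it cannot adjust the contrast between them. Even with both, it adjusts for prior users but leaves them in the outcome, so it does not restore the transition reading.

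**Working it through.** The plan states no prior-use share, outcome rate, alpha or power for this comparison, so there is no figure of its own to reproduce. What follows is illustrative. From the documents: anticipated cohorts of 4,636 (WA) and 779 (OH). Assumed: everything else. The outcome is treated as one binary result per worker, with no other covariates and no GEE clustering.

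**Set-up.** Let p be the share of prior users in a state, q1 their composite risk and q0 the risk in opioid-naive workers.

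State risk = p × q1 + (1 − p) × q0

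OR = [WA risk / (1 − WA risk)] / [OH risk / (1 − OH risk)]

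**1. No program effect, unequal shares.** q0 = 5% in both states; p = 2% in WA and 6% in OH.

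| q1 | WA risk | OH risk | OR | OR with shares reversed |
|---|---|---|---|---|
| 20% | 0.02×0.20 + 0.98×0.05 = 0.053 | 0.06×0.20 + 0.94×0.05 = 0.059 | (0.053/0.947)/(0.059/0.941) = 0.89 | 1.12 |
| 40% | 0.02×0.40 + 0.98×0.05 = 0.057 | 0.06×0.40 + 0.94×0.05 = 0.071 | (0.057/0.943)/(0.071/0.929) = 0.79 | 1.26 |
| 80% | 0.02×0.80 + 0.98×0.05 = 0.065 | 0.06×0.80 + 0.94×0.05 = 0.095 | (0.065/0.935)/(0.095/0.905) = 0.66 | 1.51 |

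The last column is the reciprocal of the one before it.

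**2. No program effect, equal shares.** The two state risks are identical, so the OR is 1.00 whatever p and q1 are. Prior users still supply many of the events. With p = 10% in both states:

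- q1 = 20%: 0.10×0.20 / 0.065 = 31% of events
- q1 = 40%: 0.10×0.40 / 0.085 = 47% of events

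**3. True effect, equal shares.** Assume an OR of 0.60 in naive workers and no effect in prior users. The naive OH odds are 0.05/0.95 = 0.0526. Multiplied by 0.60 this is 0.0316, a naive WA risk of 3.06%.

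- p = 5%, q1 = 20%: OH 0.0575, WA 0.0391, whole-cohort OR 0.67
- p = 10%, q1 = 40%: OH 0.0850, WA 0.0676, whole-cohort OR 0.78
- p = 20%, q1 = 40%: OH 0.1200, WA 0.1045, whole-cohort OR 0.86

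At an assumed two-sided 5% level, approximate power in these three cases is 64%, 43% and 26%. Restricting to naive workers leaves 740 + 4,404, 701 + 4,172 and 623 + 3,709 workers (OH + WA). Power is then 74%, 72% and 67%. Under these assumptions the restriction loses workers but gains power.

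**The case against.** **The PDMP route is better than the words 'if available' suggest.** OH has a stated individual look-up fallback, for a cohort of about 779. This stands, and it lowers the chance that the covariate fails. It does not settle the matter, because Topic D still treats feasibility as open in both states and names no substitute.

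**Prior users do not automatically count.** The primary outcome uses WC billing, so opioids paid for by others do not enter it. This stands: prior users can count, not must. The WA payment rule also covers any opioid billed beyond six weeks, so prior users there are subject to the program.

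**Hypothesis 1 is about unsafe prescribing, not new onset.** This partly stands, so a new-user restriction fits a sensitivity analysis better than a redefinition of the primary cohort. But Topic B itself gives transition as the purpose of the model, and confounding by prior use would matter under either reading.

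**The covariate list is provisional.** True, which makes an addition easy; it does not supply one.

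**A reader might infer that the bias favours WA.** One route is to set 779 expected OH workers against this statement in Section 4: "In the BWC State Fund, there is an approximate annual prevalence of 20,000 opioid users". That figure is a prevalence across the whole fund, at any time since injury. The 779 are new claims with an early fill. Their ratio does not give the share of new claimants with prior use, and no comparable WA prevalence is given. Another route is the program dates, July 2013 in WA and March 2019 in OH, which might suggest that more long-term users remained in OH. That is conjecture: the documents report no prior-use share in either state.

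**A reader might also infer that Hypothesis 2A is equally exposed.** It is not. Topic I is confined to WA, where PDMP linkage is routine.

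**Conclusion.** The gap is real and worth closing before analysis. The plan aims at transition, admits workers who may already be on opioids, and leaves the only named adjustment to data it has not secured. The likely result is either confounding of unknown direction or dilution, depending on whether prior-user shares differ by state.

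The size cannot be fixed from the documents. Under the stated assumptions, a modest imbalance of 2% against 6% moves a null odds ratio to between 0.89 and 0.66, or to between 1.12 and 1.51 if reversed. Equal shares leave it at 1.00. These are unadjusted figures; other covariates might absorb part of the difference. They also assume that prior users' chronic-phase opioids are paid by WC. Confidence is medium, because the shares and risks are unknown and PDMP data may yet arrive from both states.

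**What to change.** In Topic B:

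1. Use Claimant ID to obtain WC pharmacy bills on cohort members' earlier claims for the 3 months before injury. Derive a flag for any prior WC-paid opioid, and put it in the outcome model and the propensity score whether or not PDMP data arrive.
2. Pre-specify a sensitivity analysis that repeats the composite model in workers with no prior fill. Use all-payer PDMP fills to define prior use where both states supply them, and the WC flag otherwise.
3. If PDMP data are missing in either state, state that prior use paid by other sources is uncontrolled in the WA-OH comparison.

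In Topic I, add only the opioid-naive sensitivity analysis.

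**Cost.** An added pharmacy extract is needed. The 2010-2020 time series in Topic A uses bills only up to three months after each injury, so it would miss later bills on an older claim, and it does not cover claims before 2010. The sensitivity sample is slightly smaller: at the assumed 2% and 6%, about 93 of 4,636 workers in WA (4,636 × 0.02) and 47 of 779 in OH (779 × 0.06) would leave. The WC flag misses prior use paid by others, which is why the limitation in item 3 is needed.
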